5. SUBJECTS

Subjects

It is anticipated approximately 16 participants will be treated per year (5-6 per study site) during the first three years of the study. We expect to screen 80 subjects to get 48 subjects enrolled and 38 to complete the study (potential dropout rate of rate of 20%). Subjects will be between the ages of 10-25 y old at time of enrollment (11-27 y at end of intervention), and we expect each patient to complete the 56 week study.

Recruitment

We will recruit patients from the endocrinology clinics at the three sites, and will accept referrals from other endocrine providers. We will be advertising the study to other Pediatric Endocrinologists through a secure message board.

Enrollment

The PI at each site will screen and consent/assent subject or designate other qualified study staff to do so. Qualified participants will start with a 2-week placebo run-in to test adherence to the protocol. Immediately afterwards, subjects will be assigned treatment using a permuted-block randomization (1:1) with varying block sizes constructed by the Children's Core for Biomedical Statistics (CCBS) of Seattle Children's Research Institute (SCRI) stratified by study site, two age groups (10-14y, 15-25y), and gender. This is a double-blind study (participants and investigators both blinded). The study statistician will be blinded as well; a second statistician not involved in the conduct of the study will be responsible for the final preparation of the randomization scheme. Only the independent CCBS statistician and dispensing pharmacy at each site will know assigned study medications. It is anticipated approximately 16 participants will be treated per year (5-6 per study site) during the first three years of the study. We expect to screen 80 subjects to get 48 subjects enrolled and 38 to complete the study (potential dropout rate of rate of 20%). As we would expect many of these participants to be prepubertal as they have hypogonadotropic hypogonadism by virtue of their disease, pubertal status will not be used as an inclusion or exclusion criteria for the study.

Inclusion Criteria

- Age 10-25 years at time of enrollment
- Diagnosis of hypothalamic obesity with age- and sex adjusted BMI $\geq 95\%$ or BMI $\geq 30 \text{ kg/m}^2$ if over 18 y
- History of craniopharyngioma or another tumor located in the hypothalamic area
- Hypothalamic lesion documented by neuroradiology
- ≥ 6 months post-surgical or radiation treatment
- Weight stable or increasing over 3 months prior to screening visit
- Stable hormone replacement for at least 3 months prior to screening visit

Exclusion Criteria

- Renal impairment (GFR<60 ml/min/1.73m² using the Schwarz formula¹¹⁶)
- History of gastroparesis; pancreatitis or gallstones (unless status post cholecystectomy)
- Family history of multiple endocrine neoplasia type 2 or familial medullary thyroid carcinoma metabolic disorders
- Any insulin-treated diabetes mellitus, poorly controlled type 2 diabetes (HbA1c $\geq 10\%$), or any other chronic serious medical conditions such as CVD, malignancy or hematologic disorder, complicated syndromic disorder, or psychiatric disorders (schizophrenia, major depression, history of suicide attempts)
- Calcitonin $>50 \text{ mg/L}$ at screening
- Initiation of weight loss medications within 3 months of screening visit
- Previous donation of blood $>10\%$ of estimated blood volume within 3 months prior study
- Current warfarin use
- Current use of any other GLP1RA
- Untreated thyroid disorder or adrenal insufficiency

- History of bariatric surgery or planned bariatric surgery until end of study
- Pregnancy, lactation or expectation to conceive during study period
- Subject unlikely to adhere to study procedures in opinion of investigator
- Subject with contraindication to neuroimaging by MRI

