The proposed study is a multi-site 36-week double-blind, placebo-controlled randomized trial followed by an 18-week open label extension with all patients receiving the GLP1RA treatment. Therefore, each subject will be treated for a total of 54 wk. Subjects will be required to travel to one of three research sites (Seattle, Nashville, St. Paul). A flowchart for scheduled study visits (SVs) is outlined below. Before study start, there will be an investigator kickoff and training meeting guided by [name] from Seattle Children's to coordinate and align all assessments and interventions. In addition, Seattle Children's radiology center will provide standardized protocols to the other two imaging centers for consistent imaging techniques and analyses. During the study and after ending the intervention, there will be bimonthly investigator phone or video conferences.

Time Frame/Duration

The timeline for research activities is four years. This is outlined as: Years 1-3: Enrollment and treatment at 3 study sites. Years 3 and 4: hormonal assays. Year 4: completion of final data analyses.

Each patient will be in the study for 56 weeks, including the screening visit.

Data Requirements

A database will be designed for this study using REDCap (Research Electronic Data Capture) hosted at the Institute of Translational Health Sciences of which Seattle Children's and University of Washington are partners. REDCap is a secure, web-based application designed to support data capture for research studies, providing validated data entry, audit trails, and mechanisms for securely importing and exporting data. It will reside on a secure server with exclusive access by research personnel at all study sites. Access is tailored for specific roles to maintain blinding. Subjects are identified with a study identification number.

Study Measures

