Currently available GLP1RAs include a variety of schedules: twice daily (exenatide), once daily (liraglutide), and once weekly (exenatide, albiglutide, and dulaglutide). Alternatively, levels of native GLP-1 can be increased by inhibiting dipeptidyl peptidase 4 (DPP-4), a protease that rapidly degrades native GLP-1. However, DPP-4 inhibitors do not inhibit appetite or lead to body weight reduction.

Liraglutide, the active ingredient in Saxenda®, was recently approved as a weight loss medication showing a 7.3% decrease in body weight over a 56 wk trial in adults with severe obesity.^{104,105}

However, this drug has not been made available for use in pediatric studies and this is not expected to change in the near future (personal communication with Medical Director, Obesity at Novo Nordisk Inc). Therefore, we decided to use the extended-release GLP-1 receptor agonist ExQW which is also advantageous as it requires only weekly injections, addressing some of the adherence and side effect issues that could pose barriers to therapy. This drug contains exenatide, which is a 39-amino-acid synthetic version of exendin-4 that shares approximately 50% sequence identity with human GLP-1. In previous studies of adults with T2DM, ExQW showed slightly larger reductions in body weight compared with twice daily exenatide, although this difference was statistically not different.¹⁰⁶ Mild to moderate GI adverse events were common in previously tested three GLP-1 agonists, and were least frequent with ExQW.^{33,106-108} ExQW contains exenatide encapsulated in microspheres consisting of a medical-grade biodegradable poly-(d,l-lactide-co-glycolide) polymer, which has been used in other medical applications since 1984, and allows for slow, continuous release of the active agent into circulation following injection.^{34,109} ExQW will be started at 2 mg subcutaneously once weekly.

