6. STUDY PROCEDURES

For the placebo-controlled portion of the trial, each subject will have a screening visit and 4 study visits (weeks 0 [baseline], 6, 18, 36 [end of randomized trial]). Week 36 will also mark the beginning of the open label extension phase which will continue until week 54.

Screening Visit: The study will be explained to patients and their families and written consent/assent will be obtained. Medical history and concomitant medications will be documented. Vital signs will be recorded, including blood pressure, heart rate, respiratory rate and temperature. Body weight (lightly clothed) and height will be measured with a calibrated electronic scale and calibrated stadiometer. Hip and waist circumference measurements will be completed. A physical exam including Tanner staging will be done. This visit will also include:

- Blood draw for safety labs (electrolytes, CBC, lipase, amylase, glucose, transaminases (ALT, AST), creatinine, hemoglobin A1c, and thyroid hormones [TSH and free T4, or in patients with panhypopituitarism, free T4 only])
 - Blood for carcinoembryonic antigen (CEA) and calcitonin samples
- Blood for DNA extraction will be obtained for genetic markers (only at select sites)
- Urine pregnancy testing (HCG) will be done
- Instructions for 24h dietary recall.

Sexually active female participants are required to use birth control, unless they have documented gonadotropin deficiency.

Parents and participants (if appropriate) will be taught how to mix and inject the study medication. Parents/participants should perform a return demonstration before mixing the actual study medication. All teaching will be documented. Prior to leaving the clinic, parents/participants will inject the first dose of study medication under supervision. Dosing will be documented on the dosing log. Participants will be dispensed 1 more vial of study medication (placebo) to be administered at home the following week. The dose will be identical to the dosing provided in the blinded portion of the trial.

[figure not shown]

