Study Visits (SVs): After the initial screening visit, there will be 5 study visits (see overview and measures in **Fig. 1**) to assess adherence, drug safety, outcomes, and to distribute the drug or placebo. Hypoglycemia medications will be adjusted as needed. During the duration of the treatment, subjects with persistent abdominal pain and nausea/vomiting will discontinue study medication and be evaluated for acute pancreatitis and cholecystitis. In children, most adverse effects are mild GI effects that are transient.¹¹⁷ Subjects not tolerating their current dose will be discontinued from study at PI's discretion. Study medication will resume if and only if no significant adverse event is found and subjects concur. Subjects need to fast and refrain from exercise for ten hours prior to study visits for fasting blood draws. Physical exams including Tanner staging, and inspection of injection sites will be done at all visits (except no Tanner staging at 6 weeks visit). If a subject withdraws from the study or is withdrawn by an investigator for any reason, subjects will be asked to complete SV4 study procedures, not including the DEXA scan.

Other measures assessed at SVs (see Fig. 1):

- Questionnaires (eating, activity): SVs 1, 3, 4,
- 24h dietary recall-done the week prior to : SVs 1, 3, 4, 5
- Anthropometry: SVs 1, 2, 3, 4, 5
- Vital signs: SVs 1, 2, 3, 4, 5
- Actimetry: SVs 1, 3, 4
- Blood for metabolic outcomes: SVs 1, 3, 4, 5
- OGTT: SVs 1, 3, 4
- Energy intake at free buffet meal: SVs 1, 4
- Whole body DEXA in order to evaluate body composition: SVs 1, 4
- DLW energy balance assessment: SVs 1, 4
- ECGs: SVs 1, 3, 4, and 5
- Safety labs (electrolytes, CBC, lipase, amylase, glucose, ALT, AST, creatinine, hemoglobin A1c, and thyroid hormones): SVs 2, 3, 4, 5
 - Additional serum will be obtained at all sites and stored at a central location (SCRI Seattle) for future use (3 ml in case anti-exenatide antibodies will need to be assessed)
- CEA: SVs 3, 4, 5
- Calcitonin: SV 5
- MRI (if needed): SV 1

Weekly Contact: Research participants will be contacted weekly by telephone/email to assess for potential adverse events, concomitant medications, and compliance with dosing. Participants will also be reminded about their urine collections, diet recalls, and return of the accelerometer during these phone calls.

Visit Schedule:

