7. RISKS/BENEFITS

Potential Risks

The subjects participating in this study will be exposed to physical, psychological, and financial risks. Participation in all aspects of the research will be voluntary. Subjects, their parents or their legal guardians will be advised that they can withdraw without penalty or refuse participation in any portion of the study at any time. Overall there are moderate risks to subjects. There is a risk of breach of patient confidentiality.

Potential risks to the participants enrolled in the study include:

1. Discomfort from hunger due to 10h fasting until 8:30 AM at four of the study visits (week 0, 18, 36, 54).
2. Pain, minor injury (bruising), nausea, infection or the development of a localized inflammation (thrombophlebitis) from placement of an intravenous catheter and obtaining serial blood samples. Rarely some people faint.
3. Loss of a small volume of blood (16-20 ml at the screening visit and week 54 visits; 9-13 ml at week 6 visit; and 32-36 ml per OGTT study visit at weeks 0, 18, and 36).
4. Patients will have a brain MRI if there was no recent MRI within 6 months prior to enrollment in the study. Potential risks from the MRI include anxiety, claustrophobic reactions or discomfort due to high noise, need to maintain a fixed posture, and/or interference between unidentified metal inside or outside the body and the scanner. The overall safety of MRI is well established. All MRI pulse sequences used are within FDA guidelines for time-varying magnetic fields. Additionally, echo-planar imaging (EPI) conveys the potential for damage to subjects' hearing as the EPI gradients produce noise in the 120 dB intensity range. Sound attenuating headphone

decrease the sound delivered by 40 dB, greatly reducing the intensity of the sound. Participants will be able to hear verbal commands given via the sound attenuating headphones that are at the volume level of conversational speech.

5. This research study involves exposure to very low dose radiation from two DEXA whole body scans. Each DEXA exposes the patient to the equivalent of less than one day of background radiation.
6. There is a slight risk of skin irritation during an ECG from the electrodes or gel that is used.
7. Participants may find it bothersome to answer the investigator's questions.

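### The calcitonin exclusion is set in mg/L; if the laboratory reports ng/L or pg/mL, it excludes no one as written, so the unit needs confirming

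*Combined protocol and SAP*

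**What the plan says.** Section 5, under Exclusion Criteria, lists "Calcitonin $>50 \text{ mg/L}$ at screening" as a reason not to enrol. Calcitonin comes up in three other places in the combined protocol and SAP, none of which gives a unit, a limit, an assay or a reference range:

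- Section 6, Screening Visit, lists the draw: "Blood for carcinoembryonic antigen (CEA) and calcitonin samples".
- Section 6, in the list of other measures at study visits, has "Calcitonin: SV 5".
- Section 7, Thyroid AEs, says calcitonin is included as a safety measure. It cites the boxed warning on C-cell tumors seen in animals and notes that no such relationship has been documented in humans.

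Section 5 expects 80 subjects to be screened and 48 enrolled.

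**The concern.** An eligibility limit has to be one that a laboratory result could exceed. A milligram-per-litre limit for a circulating peptide hormone looks like a unit slip, with mg written for ng. Read literally, the criterion would then take no part in deciding who receives the drug.

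The screening sample is drawn because of the C-cell concern in Section 7, and this criterion is what turns its result into an enrolment decision. It applies to both arms: enrolment starts at age 10, and every subject receives exenatide in the open-label extension. In the visible text the only later calcitonin draw is at study visit 5. That visit is week 54 by inference: Section 6 places four visits at weeks 0, 6, 18 and 36, and Section 7 gives blood volumes of "16-20 ml at the screening visit and week 54 visits", although its Blood draws paragraph once labels visit 5 as 36 weeks. The visit list may be incomplete, because Figure 1 is not shown and nothing follows the Visit Schedule heading.

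**Working it through.** **Inputs**

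- Limit: 50 mg/L (Section 5, Exclusion Criteria).
- Expected number screened: 80 (Section 5).
- Weekly study-drug dose, used only for scale: "ExQW will be started at 2 mg subcutaneously once weekly" (Section 4, Rationale for Medication).
- Reporting unit for serum calcitonin: not in the documents. Assumed to be ng/L or pg/mL.

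The limit is stated, not derived, so there is no calculation in the plan to reproduce. The check is a unit conversion.

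**Step 1. Convert the limit.** 1 mg = 1,000 micrograms = 1,000,000 ng, and 1 ng/L = 1 pg/mL.

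- 50 mg/L × 1,000 = 50,000 micrograms/L.
- 50 mg/L × 1,000,000 = 50,000,000 ng/L = 50,000,000 pg/mL.

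**Step 2. Compare it with a range of results.** The documents give no range, so these values are assumptions chosen to span a wide interval.

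| Assumed result | Limit ÷ result |
|---|---|
| 1,000 ng/L | 50,000,000 / 1,000 = 50,000 |
| 1,000,000 ng/L | 50,000,000 / 1,000,000 = 50 |

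Across this range no result comes near the limit, so the criterion excludes 0 of the 80 subjects expected at screening.

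**Step 3. Compare it with the units that might have been intended.**

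| Intended limit | Limit as transcribed ÷ intended limit |
|---|---|
| 50 ng/L (50 pg/mL) | 1,000,000 |
| 50 micrograms/L | 1,000 |
| 50 mg/L | 1 (no change) |

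A lost micro sign would not settle the matter: 50 micrograms/L is 50,000 ng/L, still 1,000 times 50 ng/L.

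**Step 4. Scale check from the protocol's own figures.** 2 mg ÷ 50 mg/L = 0.040 L = 40 mL. At the stated limit, 40 mL of serum would hold as much calcitonin by mass as one weekly dose of the study peptide. This shows the order of magnitude only. It compares different peptides, and a dose with a concentration, so it says nothing about an assay range.

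**The case against.** The strongest reply is that no error in the protocol itself has been shown. The line was read from a PDF by a program, and a single misread letter would produce it. Nothing in the text points to a misreading, and other units in the document, such as mU/L in Table 3, come through sensibly, but the possibility stands until someone looks at the page.

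The reporting unit is also an assumption from outside the documents, as is the suggestion that ng/L was meant. That stands too, and the conclusion is conditional on it.

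The consequence may be nil. Recruitment runs through endocrinology clinics, whose staff would probably apply 50 in the laboratory's own unit, and a kickoff meeting is planned "to coordinate and align all assessments and interventions". A corrected limit might exclude nobody either, so 0 of 80 does not measure harm. Other safeguards do not depend on this unit: the exclusions for "Family history of multiple endocrine neoplasia type 2 or familial medullary thyroid carcinoma", for malignancy and for "Untreated thyroid disorder or adrenal insufficiency", and CEA at screening and at study visits 3, 4 and 5. The separate Data and Safety Monitoring Plan was not available and may say more.

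These points keep the matter minor but do not remove it. None of the visible safeguards is a calcitonin limit, and no other part of the text corrects the unit. A limit that works only because each site silently reinterprets it is still wrong as written.

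**Conclusion.** The point holds as a minor one, with medium confidence. As transcribed, the only calcitonin limit in the available documents is 50,000,000 ng/L, and under the assumed reporting unit it could not exclude a screened subject. This rests on two conditions: that the source page does print mg/L, and that the screening laboratory reports in ng/L or pg/mL. The fold differences describe the gap between units, not damage to the trial. How many subjects a corrected limit would exclude is unknown and could be zero. The point covers this one criterion and leaves sample size, power and the planned analyses unchanged.

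**What to change.** Check the source page. If it reads ng/L, nothing needs to change.

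If it reads mg/L:

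1. Correct the criterion to the intended unit. This is probably >50 ng/L (50 pg/mL), but the sponsor should confirm it against the unit the screening laboratory reports.
2. Give all three sites the same limit and unit, for example at the kickoff meeting.
3. Review any screening calcitonin results already obtained against the corrected limit.

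The cost is a look at one page and, if mg/L is confirmed, a one-unit minor amendment and a review of existing results. No new samples are needed.

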6. STUDY PROCEDURES

For the placebo-controlled portion of the trial, each subject will have a screening visit and 4 study visits (weeks 0 [baseline], 6, 18, 36 [end of randomized trial]). Week 36 will also mark the beginning of the open label extension phase which will continue until week 54.

Screening Visit: The study will be explained to patients and their families and written consent/assent will be obtained. Medical history and concomitant medications will be documented. Vital signs will be recorded, including blood pressure, heart rate, respiratory rate and temperature. Body weight (lightly clothed) and height will be measured with a calibrated electronic scale and calibrated stadiometer. Hip and waist circumference measurements will be completed. A physical exam including Tanner staging will be done. This visit will also include:

- Blood draw for safety labs (electrolytes, CBC, lipase, amylase, glucose, transaminases (ALT, AST), creatinine, hemoglobin A1c, and thyroid hormones [TSH and free T4, or in patients with panhypopituitarism, free T4 only])
 - Blood for carcinoembryonic antigen (CEA) and calcitonin samples
- Blood for DNA extraction will be obtained for genetic markers (only at select sites)
- Urine pregnancy testing (HCG) will be done
- Instructions for 24h dietary recall.

Sexually active female participants are required to use birth control, unless they have documented gonadotropin deficiency.

Parents and participants (if appropriate) will be taught how to mix and inject the study medication. Parents/participants should perform a return demonstration before mixing the actual study medication. All teaching will be documented. Prior to leaving the clinic, parents/participants will inject the first dose of study medication under supervision. Dosing will be documented on the dosing log. Participants will be dispensed 1 more vial of study medication (placebo) to be administered at home the following week. The dose will be identical to the dosing provided in the blinded portion of the trial.

[figure not shown]
Study Visits (SVs): After the initial screening visit, there will be 5 study visits (see overview and measures in **Fig. 1**) to assess adherence, drug safety, outcomes, and to distribute the drug or placebo. Hypoglycemia medications will be adjusted as needed. During the duration of the treatment, subjects with persistent abdominal pain and nausea/vomiting will discontinue study medication and be evaluated for acute pancreatitis and cholecystitis. In children, most adverse effects are mild GI effects that are transient.¹¹⁷ Subjects not tolerating their current dose will be discontinued from study at PI's discretion. Study medication will resume if and only if no significant adverse event is found and subjects concur. Subjects need to fast and refrain from exercise for ten hours prior to study visits for fasting blood draws. Physical exams including Tanner staging, and inspection of injection sites will be done at all visits (except no Tanner staging at 6 weeks visit). If a subject withdraws from the study or is withdrawn by an investigator for any reason, subjects will be asked to complete SV4 study procedures, not including the DEXA scan.

Other measures assessed at SVs (see Fig. 1):

- Questionnaires (eating, activity): SVs 1, 3, 4,
- 24h dietary recall-done the week prior to : SVs 1, 3, 4, 5
- Anthropometry: SVs 1, 2, 3, 4, 5
- Vital signs: SVs 1, 2, 3, 4, 5
- Actimetry: SVs 1, 3, 4
- Blood for metabolic outcomes: SVs 1, 3, 4, 5
- OGTT: SVs 1, 3, 4
- Energy intake at free buffet meal: SVs 1, 4
- Whole body DEXA in order to evaluate body composition: SVs 1, 4
- DLW energy balance assessment: SVs 1, 4
- ECGs: SVs 1, 3, 4, and 5
- Safety labs (electrolytes, CBC, lipase, amylase, glucose, ALT, AST, creatinine, hemoglobin A1c, and thyroid hormones): SVs 2, 3, 4, 5
 - Additional serum will be obtained at all sites and stored at a central location (SCRI Seattle) for future use (3 ml in case anti-exenatide antibodies will need to be assessed)
- CEA: SVs 3, 4, 5
- Calcitonin: SV 5
- MRI (if needed): SV 1

Weekly Contact: Research participants will be contacted weekly by telephone/email to assess for potential adverse events, concomitant medications, and compliance with dosing. Participants will also be reminded about their urine collections, diet recalls, and return of the accelerometer during these phone calls.

Visit Schedule:

